Role of Virtual Reality (VR) in Decreasing Pain and Anxiety in Patients with Sickle Cell Disease (SCD) and Cancer

Protocol Summary

NCT03387033

1. Protocol Title: Role of Virtual Reality (VR) in Decreasing Pain and Anxiety in Patients with Sickle Cell Disease (SCD), Cancer, and Bone Marrow Transplant (BMT) Patients

2. Purpose of the Study: We propose implementing a feasibility study of the use of VR in patients with SCD, cancer, and bone marrow transplant patients. We plan to assess pain as well as anxiety and depressive symptoms prior to the session as well as following the session for inpatients and outpatients with SCD, malignancy, and patients undergoing/who underwent BMT. The sessions will include a ten-minute relaxation response introductory narrative segment (deep breathing and mindfulness) followed by a ten-minute narrated and immersive VR. **We hypothesize the use of VR will not only be feasible, but will also decrease pain, anxiety and depressive symptoms in hospitalized patients and outpatients with SCD, cancer, and BMT patients.**

3. Background & Significance: Pain, anxiety and depression contribute significantly to health care visits and subsequently contribute substantially to the cost of the healthcare system. In 2009-2010, visits related to mental health as primary concern accounted for over 63 million visits in the outpatient setting.¹ Patients with sickle cell disease (SCD) often have complicated courses while hospitalized and often deal with pain, anxiety, and depression. SCD is a chronic blood disorder with patients typically experiencing daily pain with frequent hospital admissions for worsened acute pain. Cancer and BMT patients also commonly deal with pain related to primary malignancy, side effects of chemotherapy, transplant complications, etc. They may also have symptoms of anxiety and depression in the setting of chronic illness.

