They will then listen to a ten-minute relaxation response recording by [name] on an iPhone. Following this, the image on Provata VR will be opened, the narration of the VR image by [name] will be started on the iPhone, and the VR headset secured. The patient should be sitting or lying down for the VR portion of the session to decrease the risk of injury. The audio narration will play while the patient is viewing the VR image. The study team will be supervising the patient while the headset is in use. No patient data will be stored on the iPhone, it simply allows the patient to view the VR image through the VR headset with narration by [name]. During the entire session, patients will also wear an Apple iWatch to passively record objective data such as heart rate through the Health app. For 30 minutes prior to and following the session, patients will also wear the Apple iWatch.

The patients will first be provided a consent form and consented. They will have the opportunity to ask questions prior to and following consent. They will subsequently fill out a GAD-7 (Generalized Anxiety Disorder) and PHQ-9 (Patient Health Questionnaire) form. They will complete the session described above. Patients will also provide an initial pain score and answer questions through the TRU-Pain app. Following this, patients will complete another GAD-7, PHQ-9, pain score, Presence Questionnaire, Feasibility Questionnaire, Patient's Global Impression of Change (PGIC) form, and answer questions in the TRU-Pain app. Patients will then be able to ask questions/provide further feedback.

5. Selection of Subjects: A total of 60 subjects, including inpatients and outpatients with SCD, malignancy, and patients undergoing/who underwent BMT. Approximately half of these patients will be inpatient and half will be outpatient. These patients must have a diagnosis of chronic or acute pain (current pain or baseline pain score >0) or have at least one symptom of anxiety or depression as measured by the GAD-7 or PHQ-9 questionnaires (positive response to any question).

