9. Study Interventions: A 30 minute session with ten-minute relaxation response and ten-minute narrated VR with surveys before and after session. Patients will wear an Apple iWatch to passively record objective data. Patients will also wear an Apple iWatch for 30 minutes prior to and 30 minutes following session to record objective data passively.

10. Risk/Benefit Assessment: This study involves minimal risk given the imagery/narrative used will likely either be seen in a neutral or positive light. Loss of PHI and breach of patient confidentiality are possible risks. The potential benefits include improvement in anxiety and/or depressive symptoms. The results of this study will be critical as feasibility and pilot analysis to use for power analysis and future grant submissions with additional collaborators. Minimal risk to using TRU-Pain app given the data gathered is de-identified.

11. Costs to the Subject: The subjects will not have any costs associated with the study other than the utilization of approximately 90 minutes of their time for the session.
Routine medical care will be charged to the subject or their insurance company.

12. Data Analysis & Statistical Considerations: The endpoints of the study are feasibility of 30-minute VR sessions and change in pain, GAD-7, and PHQ-9 scores. Study personnel with assistance of Duke statistician if needed will analyze the data to determine if any significant change in GAD-7 and PHQ-9 was noted in any group with the study intervention. This data/outcome of the study will be used to power future studies.

A sample size of approximately 60 is appropriate given this is a feasibility study. Within 1 year, these patients hopefully will be reached.

13. Data & Safety Monitoring: The data will be obtained with the use of Duke Box to maximize the protection of each patient's data. Objective data collected on the Apple iWatch

Role of Virtual Reality (VR) in Decreasing Pain and Anxiety in Patients with Sickle Cell Disease (SCD) and Cancer

Protocol Summary

will be uploaded to Citrix Sharefile via the TRU-Pain HKO app and will subsequently be transferred to Duke Box. Data gathered from the TRU-Pain app will be sent to Citrix Sharefile and Duke Box as well. There will not be an independent data monitoring committee for this study. The PI will review and sign off on all adverse events and any problems. These will be reported to the IRB in accordance with HRPP policies.

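### Does admitting patients who score 0 on an endpoint scale require section 12 to plan a separate analysis of those above 0?

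*Combined protocol and SAP*

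**What the plan says.** Section 5 (Selection of Subjects) joins its entry routes by a plain "or": pain, or one positive item on either questionnaire ("current pain or baseline pain score >0) or have at least one symptom of anxiety or depression as measured by the GAD-7 or PHQ-9"). Someone admitted for pain may score 0 on both GAD-7 and PHQ-9. Someone admitted on a single GAD-7 item may score 0 on pain and on PHQ-9.

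Section 12 lists the endpoints: "The endpoints of the study are feasibility of 30-minute VR sessions and change in pain, GAD-7, and PHQ-9 scores". The only analysis sentence concerns the two questionnaires: the data will be examined "to determine if any significant change in GAD-7 and PHQ-9 was noted in any group with the study intervention". No test, summary statistic or baseline-score subset is named. On later use, section 12 says "This data/outcome of the study will be used to power future studies", and section 10 says "The results of this study will be critical as feasibility and pilot analysis to use for power analysis and future grant submissions".

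The hypothesis in section 2 is that VR will "decrease pain, anxiety and depressive symptoms in hospitalized patients and outpatients with SCD, cancer, and BMT patients". It refers to the whole patient mix and not to those with a given symptom. Section 4 collects pain, GAD-7 and PHQ-9 before and after the session.

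**The concern.** A decrease from 0 is impossible. If a share f of patients starts at 0 on a scale, they pull the mean change on that scale towards 0, by a factor of roughly (1 − f). An investigator who later plans a trial only in patients with the symptom, and takes the all-patient change as the expected effect, would make that trial too large. The factor cannot be undone from a published mean and SD unless f is reported.

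Pain is probably the scale least affected: section 3 says "SCD is a chronic blood disorder with patients typically experiencing daily pain" and "Cancer and BMT patients also commonly deal with pain related to primary malignancy". For mood in cancer and BMT patients the same section says only that symptoms may be present, so zeros on GAD-7 and PHQ-9 are plausible. Since powering later work is a declared purpose, the silence of section 12 looks like a gap in the one product the pilot is meant to deliver.

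**Working it through.** **1. The plan's own figure.** There is nothing to reproduce. Section 12 gives about 60 patients, justified only by the feasibility aim, with no effect size, SD, alpha or power. It gives no f and no expected change, so every figure below is illustrative.

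**2. Simple dilution.** Assume that patients above 0 change by 1.0 with SD 2.0 (0.5 SD) and that patients at 0 do not change. For all patients:

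- mean = 1 − f
- variance = 4(1 − f) + f(1 − f)
- required size is proportional to variance/mean², so relative to a trial in patients above 0 the ratio is (1 + f/4)/(1 − f)

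| f | ratio | per arm (two-sided 0.05, power 80%) |
|---|---|---|
| 0 | 1 | 63 |
| 10% | 1.025/0.9 = 1.14 | 72 |
| 20% | 1.05/0.8 = 1.31 | 83 |
| 40% | 1.1/0.6 = 1.83 | 116 |
| 50% | 1.125/0.5 = 2.25 | 142 |

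This is an error only if the later trial recruits by symptom. If it enrols the same mix, the all-patient figure is the right one, and 63 per arm would give power of 75%, 69%, 55% and 46% at these four values of f.

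**3. Sampling error of the pilot.** With a change of 1.0, SD 2.0 and n = 60, the 95% half-width is t(0.975, 59) × 2/√60 = 0.517, so the interval is 0.48 to 1.52. Sizing from its ends gives 1/1.517² = 0.43 and 1/0.483² = 4.3 times the correct number. Every ratio in the table lies inside that range.

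**4. Would the change above 0 serve better?** Assumed model: a 0–10 scale; true score Normal with mean 1.5 or 3 and SD 2, clipped to the scale; measurement error SD 0.5, 1.0 or 1.5; treatment lowers the true score by 1 point or by 30%. This makes 12 scenarios, with f from 10% to 30%. The reference is a two-arm trial in patients with observed baseline above 0.

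- Sized from the all-patient change: 1.17 to 2.2 times the needed number.
- Sized from the change above 0: 0.36 to 1.04 times.
- Sized from the all-patient change divided by (1 − f), with the SD of those above 0: 0.70 to 1.11 times.

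The second figure is low because of regression to the mean: untreated patients selected for an observed score above 0 fall by 0.04 to 0.42 points. With mean 1.5, error SD 1.0 and a 1-point fall, the all-patient change is 0.62, the true between-arm difference 0.78 and the change above 0 1.03.

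**5. Adding the section 5 entry rule.** That model leaves enrolment unselected, whereas section 5 selects on the same scores that are later analysed. With three scales, entry if any is above 0, and a 1-point fall, untreated patients as a whole improve by 0.01 to 0.14 points. The true difference still lies between the two means in 32 of 36 scenarios. It falls outside in four, all with low symptom levels, f about 44% to 46% and error SD 1.0 to 1.5. In one such case the all-patient change is 0.33 and the true difference 0.28. Dividing by (1 − f) then gives 0.33/0.56 = 0.59, about twice the truth.

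**The case for a change.** The best case for a change is this. Use for power analysis is stated twice, and section 10 mentions additional collaborators, who may hold only the reported summary. Sampling error shows in a confidence interval, whereas dilution is a shift in one direction that no interval reveals. Naming the summary in advance prevents a subset from being chosen after the data are seen. The cost is two or three sentences, with no new form, procedure or patient.

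Much of this is true. The count at 0 on each scale is worth a line in the report, and a sensible analyst would put it in the baseline table unprompted. It does not follow that the plan is deficient without it. The users named in the document are the team and its collaborators, and the team holds the individual scores from which f and any threshold-specific summary can be obtained. A later trial with a higher entry threshold would in any case need its own subset, which cannot be specified now.

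Nor is a planned result above 0 harmless. A rule that later work should use the estimate closest to its own entry criterion would steer a symptom-recruited trial to the figure that usually undersizes it, the riskier error. Presenting the two means as limits around the planning effect, or correcting by (1 − f), can fail when f is high, and section 3 suggests that f is likelier to be high for the mood scales.

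**Conclusion.** No change to the plan. The entry rule does admit patients at 0 on an endpoint scale, and section 12 does not say it will count them. Following the plan as written still gives a correct result: the all-patient change estimates the change in the enrolled mix, which is what section 2 hypothesises, and feasibility and this study's own power are hardly affected. What is missing is a descriptive detail that analysts can supply from scores already collected.

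The possible cost falls on a later symptom-recruited trial that no section describes. It would be oversized 1.14 to 2.25 times for f of 10% to 50% under simple dilution, or 1.17 to 2.2 times for f of 10% to 30% in the one-scale model. Both ranges are smaller than the 0.43 to 4.3 range that comes from a pilot of 60. These sizes rest on assumed values of f, effect, SD, measurement error and a 0–10 scale, none of which the document gives. With no control arm, any expectation effect is in both the all-patient and the above-0 figures, so neither would be a clean planning input.

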Therapy is often focused on pharmacologic therapies, which are often not adequate and have side effects such as sedation. An increasing focus has therefore been placed on non-pharmacologic therapies. The scope of non-pharmacologic interventions has developed over the last several years with innovations in technology. Advances in the field of technology provide potential avenues for innovative and improved care models for our patients. Virtual reality (VR) has been recently utilized to improve anxiety and pain in a variety of patient populations including children undergoing elective surgery² and children experiencing intravenous cannulation in the Emergency Department.³ Patients with SCD, cancer, and BMT patients are groups of patients that can benefit from VR as part of their care as VR has shown effectiveness in providing remarkable non-pharmacologic therapy.

4. Design & Procedures: We will perform a feasibility and pilot study evaluating relaxation response (narration leading through deep-breathing, mindfulness, and other relaxation techniques) followed by VR in patients with sickle cell disease (SCD), cancer, and BMT patients. The VR headset (Dynamic Virtual Viewer or similar device) used will be compatible with an iPhone application titled Provata VR. The devices are provided by the study personnel. The virtual reality headset is commercially available. Different VR headsets have been used in prior studies, some compatible with computer programs and other compatible with a Samsung

Role of Virtual Reality (VR) in Decreasing Pain and Anxiety in Patients with Sickle Cell Disease (SCD) and Cancer

Protocol Summary

device. The VR session will be narrated by [name], and the image through the Provata VR mobile application has been chosen by the study team.

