6. Subject Recruitment & Compensation: Admitted patients with SCD, malignancy, or BMT patients for malignant or non-malignant disorders on the Hematology/Oncology and Bone Marrow Transplant Services in addition to outpatients with SCD, malignancy, and BMT patients for malignant and non-malignant reasons will be eligible for participation. This study will be known to Hematology, Oncology, and Bone Marrow Transplant providers. Personnel from this study will present to clinic and assess with other providers if certain patients being seen that day would fit the inclusion criteria for the study. The patient's primary care team alerts study personnel of their possible eligibility and interest. No further recruitment will likely be needed. Patients will not be compensated and the study/session involves minimal risk to the patient. As per Duke University protocol, there will be no "cold contact" whereby a patient is approached by the research team without the study having been introduced by a person known to the patient before.

Role of Virtual Reality (VR) in Decreasing Pain and Anxiety in Patients with Sickle Cell Disease (SCD) and Cancer

Protocol Summary

7. Consent Process: Risks/benefits will be explained to the patient as well as their parent(s)/guardian(s) as part of the consent process and they will have the ability to review the consent form. As much time as needed will be given for the adult patients, and the minor patients along with their parents, to make an informed decision. All questions and concerns will be answered to the potential subject's satisfaction and will verbalize understanding prior to signing the consent form.

8. Subject's Capacity to Give Legally Effective Consent: Individuals (or parents of minors) that cannot read and/or understand the requirements, and "no guarantee" of benefit of the study will not be eligible for participation. The protocol of this study targets populations that are unlikely to have impaired decisional capacity. If there is a concern for impaired capacity during the clinical interview, that patient will be excluded from the study. Parents of minors are expected to provide consent, but may be excluded from providing consent and thereby the patient excluded from the study if the parent is unable to read, cannot speak or understand English, or has impaired capacity to give legally effective consent.

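### Section 12 searches unlisted groups for significant GAD-7 or PHQ-9 change, names no all-patient estimate, and leaves the pain endpoint without an analysis

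*Combined protocol and SAP*

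**What the plan says.** Section 12 (Data Analysis & Statistical Considerations) first lists the endpoints: feasibility of the session, and change in pain, in GAD-7 and in PHQ-9. One analysis sentence follows, in which study personnel, helped by a statistician if needed, will "determine if any significant change in GAD-7 and PHQ-9 was noted in any group with the study intervention". No test, significance level or multiplicity rule is given.

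Other sections bear on how that sentence is read:

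- Section 2 hypothesises that VR "will also decrease pain, anxiety and depressive symptoms in hospitalized patients and outpatients with SCD, cancer, and BMT patients". That covers both settings, all three populations, and pain.
- Section 3 refers to SCD, cancer and BMT patients as groups.
- Section 4 describes the design: "We will perform a feasibility and pilot study evaluating relaxation response". It collects an initial pain score and another after the session.
- Section 5 sets the sample: "A total of 60 subjects, including inpatients and outpatients with SCD, malignancy, and patients undergoing/who underwent BMT". It adds a second split: "Approximately half of these patients will be inpatient and half will be outpatient".
- Section 6 opens enrolment to "Admitted patients with SCD, malignancy, or BMT patients for malignant or non-malignant disorders", so a BMT patient may also be a malignancy or SCD patient.
- Section 10 states the intended use: "The results of this study will be critical as feasibility and pilot analysis to use for power analysis and future grant submissions". Section 12 likewise says the data will power later studies.

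**The concern.** Followed as written, the sentence is an unadjusted, group-by-group search for significance on two scales. This has three consequences.

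- The more groups are searched, the likelier it is that one shows a significant change by chance.
- The estimate from the whole sample, the most precise one the study can give and the one that matches the Section 2 hypothesis, is not named.
- Pain is in the title, the hypothesis, the endpoint list and the assessments before and after the session, but has no stated analysis.

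The groups are also not fixed. Section 3 points to the three disease populations, Section 5 also divides patients by setting, and the disease labels can overlap through BMT. What counts as a group could therefore be settled after the data are seen.

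The results are meant to inform the power of later studies. For that purpose an unselected estimate with its interval is more useful than a list of groups that reached significance.

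**Working it through.** **Plan's own figure.** The sample size of about 60 is justified only by the study being a feasibility study. It is not derived from a significance level, power or precision target, so there is nothing to reproduce.

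**Inputs from the documents.** About 60 patients, each measured before and after the session; two scales in the analysis sentence; three outcomes in the endpoint list; three disease populations with no stated sizes; two settings of about 30 each.

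**Assumptions, not in the documents.** Two-sided 0.05 per test; paired t tests; normal change scores; no true change; non-overlapping groups; correlation between outcomes of 0 to 0.8; disease groups of 20 each. A significant result on any one test counts.

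**Step 1: false positives.** With k independent tests, the chance of at least one is 1 − 0.95^k.

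- Two settings × two scales, k = 4: 1 − 0.95^4 = 0.1855.
- Three disease groups × two scales, k = 6: 1 − 0.95^6 = 0.2649.
- All patients × three outcomes, k = 3: 1 − 0.95^3 = 0.1426.

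Correlated outcomes were simulated (200,000 runs per setting):

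| Analysis | Correlation 0 | 0.5 | 0.8 |
|---|---|---|---|
| Two settings of 30, two scales | 0.185 | 0.175 | 0.151 |
| Three disease groups of 20, two scales | 0.264 | 0.249 | 0.219 |
| Disease groups of 40, 10 and 10, two scales | 0.265 | 0.252 | 0.220 |
| All 60 patients, three outcomes | 0.143 | 0.126 | 0.099 |

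Unequal disease groups hardly change the result.

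**Step 2: comparison with the analysis proposed under the fix.** The fair comparator is the last row, which includes pain.

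- Disease groups: 0.264/0.143 = 1.8 at correlation 0, and 0.219/0.099 = 2.2 at 0.8.
- Settings: 0.185/0.143 = 1.3 at correlation 0, and 0.151/0.099 = 1.5 at 0.8.

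If only improvements count, which is the hypothesised direction, the values at correlations 0 and 0.8 are 0.097 and 0.077 (settings), 0.140 and 0.115 (disease groups), and 0.074 and 0.049 (all patients, three outcomes). The all-patient analysis is then lower by 2 to 3 percentage points against settings (0.097 − 0.074 = 0.023; 0.077 − 0.049 = 0.028) and by about 7 against disease groups (0.140 − 0.074 = 0.066; 0.115 − 0.049 = 0.066).

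**Step 3: precision.** The 95% CI half-width in SD units of the change score is t(0.975, n−1)/√n. This gives 0.258 at n = 60, 0.373 at n = 30 and 0.468 at n = 20.

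**Step 4: if an estimate were kept because it was significant.** Take a true mean change of 0.3 SD, again an assumption (400,000 runs). The mean of the estimates that show significant improvement is 0.571 SD at n = 20, 0.485 SD at n = 30 and 0.377 SD at n = 60. Without selection the mean is 0.30 SD at every size. Selection inflates the all-patient estimate too, but much less.

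**The case against.** The strongest reply is that this is a feasibility pilot. It has no success rule, so a stray significant result overturns nothing. That stands, and it limits the importance of the point. A reader might infer that an efficacy claim is compromised, but the plan sets no criterion for making one.

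A reader might also infer that significant results will be picked to power the next study. The documents do not support that. Sections 10 and 12 say only that the results will be used for power analysis, not which estimate will be taken. Step 4 therefore describes a risk that the wording leaves open, and the bias is an average tendency.

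It would likewise go too far to say that the groups cannot be identified at all, because Section 3 makes the three disease populations the natural reading. What remains is that Section 12 does not list them, Section 5 offers a second split, and BMT overlap is unresolved. Nor does Section 12 omit pain altogether. It lists pain as an endpoint and then gives it no analysis.

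Finally, normality is untested. Section 5 admits patients on pain or on a single positive questionnaire item, so many change scores on a given measure may be zero, especially in small groups. The percentages are therefore illustrations. The gaps in the text do not depend on them.

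**Conclusion.** The point holds in this limited form. The only analysis sentence looks for significance in unlisted groups, names no all-patient estimate and assigns pain no analysis. Nothing elsewhere in the document fills these gaps.

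Under the stated assumptions, the search is about 1.8 to 2.2 times (disease groups) or 1.3 to 1.5 times (settings) as likely to produce at least one false positive as an unadjusted all-patient analysis of all three outcomes. A disease group of 20 gives an interval nearly twice as wide as the full sample (0.468/0.258 = 1.8). The sample size is not shown to be wrong. Importance is modest, but the change is worth making because the correction costs little and serves the use that Section 10 gives the results.

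**What to change.** Replace the analysis sentence in Section 12 with wording such as:

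> Feasibility remains the first endpoint. The main analysis of symptom change is the mean pre/post change with 95% CI for each of pain, GAD-7 and PHQ-9 in all patients (paired analysis), with the number scoring zero at baseline on each measure. Results by disease group (non-overlapping, with the classification of BMT patients stated) and by setting are exploratory and are reported for every group with 95% CIs. Estimates used to power future studies are not chosen because they reached significance.

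Holm adjustment across the three outcomes is optional. It would hold the chance of any false positive to at most 5%; without it the chance is 10-14%.

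The cost is wording only, with no change to visits, data or sample size. There are two downsides. No confirmatory claim can rest on a single group. The all-patient mean on each measure is diluted by patients who entered on a different symptom and score zero there at baseline; the baseline-zero count shows how many.
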